nitric oxide which may be involved in the induction of both apoptotic and necrotic intracellular pathways. Along these lines, Funaki et al⁶⁴ have shown that apoptosis of intrahepatic bile duct epithelial cells is highly prevalent in biliary atresia liver compared to normal liver or that of patients with choledochal cyst. Moreover, Liu et al⁶⁵ reported a relationship between fas ligand (FasL) mRNA in bile duct epithelial cells and the presence of apoptosis in biliary atresia patients. Since FasL is not normally expressed in bile duct epithelial cells, this finding appeared to be specific to biliary atresia. Surprisingly, bile drainage after the portoenterostomy procedure was significantly better in patients with negative signals for FasL on bile duct epithelium than patients with positive signals, suggesting that upregulation of FasL may result in apoptotic fratricide in which bile duct epithelial cells actually injure other similar cells, or perhaps bile duct epithelium are resisting attack by infiltrating lymphocytes by posing a counterattack against Fas-expression lymphocytes⁶⁵. These provocative results emphasize interactions between macrophages, T-lymphocytes, bile duct epithelial cells, hepatocytes, and other cells in the liver which should be extended in future studies conducted by the Childhood Liver Disease Research and Education Network. The proposed serum and tissue bank outlined in this protocol should provide the specimens needed to conduct a thorough investigation into immune mechanisms in biliary atresia and idiopathic neonatal hepatitis.

Autoimmunity in Biliary Atresia. Biliary atresia shares features with several autoimmune diseases, such as the female predominance, apparent triggering by viral infection, and aberrant HLA expression in bile duct epithelium. Thus, it has been proposed that tissue injury biliary atresia may represent an autoimmune mediated process. Vasiliauskas et al⁶⁶ have reported that 10 of 11 patients with biliary atresia were positive for serum IgG and IgM antineutrophil cytoplasmic antibodies (ANCA), with higher levels of the IgM-ANCA in biliary atresia patients compared with children and adults with other liver diseases. Burch et al⁵³ studied autoantibodies in mothers of children with biliary atresia and idiopathic neonatal hepatitis, in order to test the hypothesis that maternal transfer of autoantibodies might be involved in liver and bile duct injury. The results showed that low titer anti-Rho antibodies were more common in mothers of infants with biliary atresia and idiopathic neonatal hepatitis than in controls, and that low titer antinuclear antibodies were also more common in mothers of infants with liver disease. The Childhood Liver Disease and Education Network will provide an ideal venue for future investigation of maternal factors and autoimmunity in biliary atresia.

An exciting advance in understanding risk factors for autoimmunity has been the demonstration of polymorphisms in genes that predict susceptibility of individuals to autoimmune disorders. Recent reports of Bernal et al⁶⁷ and Mitchell et al⁶⁸ have shown that TNF- α gene polymorphisms are associated with susceptibility to primary sclerosing cholangitis (58% of PSC vs 29% of controls in Bernal's study), raising the possibility that genetic differences in genes that regulate immune function, the inflammatory response, cellular regeneration, and cell survival signals may predispose to biliary injury in various clinical settings. Extending on these observations, it may well be that genes that regulate metabolism and transport of bile acids and phospholipids play a role in protection from bile duct injury in biliary atresia. Serum, DNA and tissue specimens

made available by the Childhood Liver Disease and Research Network will be instrumental in determining if genetic risk factors for autoimmunity play a role in neonatal cholestatic disorders.

Vascular Etiology. A vascular/ischemia etiology for biliary atresia has been proposed based on experimental evidence⁶⁹. Pickett et al⁷⁰ demonstrated the development of biliary obstruction following ligation of hepatic vessels in fetal sheep. Intrahepatic and extrahepatic bile ducts receive their blood supply exclusively from the hepatic arterial circulation, such that hepatic artery ischemia may lead to bile duct strictures, particularly following liver transplantation. Several investigators have demonstrated an arteriopathy in branches of the hepatic artery in the extrahepatic biliary tree of biliary atresia patients⁷¹. It has been proposed that the vasculopathy may be the primary lesion in biliary atresia; however, whether these lesions are primary or secondary to another process remains unclear.

Defective Morphogenesis: Several lines of evidence suggest that certain cases of biliary atresia are caused by defective morphogenesis of the biliary tree. Because anomalies of visceral organ symmetry are associated with biliary atresia, it is of interest that a recessive insertional mutation in the proximal region of mouse chromosome 4 or complete deletion of the inversion (inv) gene in the mouse leads to anomalous development of the hepatobiliary system in this model^{7,72}. Important work by Mazziotti et al⁷ in the inv mouse suggests that this gene plays an essential role in morphogenesis of the hepatobiliary system. It will be necessary to investigate homologues of this and other related genes in infants with biliary atresia to determine whether inherited or somatic mutations or deletions are responsible for individual cases of biliary atresia.

Intrahepatic bile development depends on interactions between mesenchyme and portal venous radicals. Primitive hepatic precursor cells differentiate into a single layer of cells that soon form a double layer as the primitive bile ductule anlage. Cells then scatter and remodel as a single layer around the lumen to form the portal tract bile duct⁸. Defects in remodeling of this ductal plate lead to the ductal plate malformation that is believed to be responsible for the liver lesion of congenital hepatic fibrosis and other bile duct dysplastic diseases. However, a number of infants with biliary atresia appear to show evidence of the ductal plate malformation on liver biopsy⁸, suggesting that interactions between hepatocyte growth factor or scatter factor and receptors such as the c-met oncogene may be defective in cases with biliary atresia and ductal plate malformation^{1,73}. Abnormalities in induction of hepatocyte growth factor during a critical period for mesenchymal/epithelial signaling or other defects in the intracellular adhesion systems could account for defective bile duct development in biliary atresia and other disorders. Further investigation of this important area of bile duct development is necessary.

Toxin Exposure: Time and space clustering of cases of biliary atresia have led to the proposal that an environmental toxin could be involved in its pathogenesis. Currently, other than infectious agents, no environmental agent has been clearly associated with biliary atresia or idiopathic neonatal hepatitis.

It is clear that the etiologies of biliary atresia and idiopathic neonatal hepatitis remain poorly understood and that the future development of new diagnostic, preventative and therapeutic strategies will require a better understanding of the causative factors. The Childhood Liver Disease Research and Education Network will provide an ideal environment in which to investigate multiple proposed etiologies simultaneously through hypothesis-directed investigations.

4. STUDY DESIGN

4.1 Design and Outcomes

This is a multi-center project to establish a prospective database of clinical information and a repository of blood and tissue samples from children with diagnoses of neonatal liver diseases, such as biliary atresia and neonatal hepatitis, in order to perform research in these important liver problems. Children will be screened and enrolled at presentation at the participating pediatric liver sites. Subjects diagnosed with biliary atresia will be followed intensively for the first year, at 18 months of age, and then annually up to 15 years of age. Other subjects diagnosed with cholestasis will be followed on the same schedule; if there is complete (clinical and biochemical) resolution of their underlying liver disease off all therapy, there will be one follow up visit within one year (preferably scheduled at the time of the next planned follow up visit or at 12 months of age, whichever is later) for data collection and to obtain blood samples. The development of a serum and tissue bank of specimens from children with various neonatal cholestatic disorders will be an invaluable tool for current and future investigations into the etiology and pathogenesis of hepatobiliary injury in the infant.

Detailed clinical data, laboratory investigations, liver biopsy specimens, and long-term follow-up of outcomes are part of the normal standard of care with respect to the diagnosis and treatment of the subjects with liver problems. This research involves the collection of diagnostic, clinical and outcome data concerning the subject, which is kept without identification (coded) in a national research database of infants with liver disease. Samples of blood and urine will be obtained for later research analysis, whenever possible, at the time of clinically indicated blood draws or when there is IV access for a clinical procedure. When liver biopsy specimens are obtained for diagnostic purposes, any liver biopsy specimen in excess of that needed for diagnostic use will be sent to the tissue repository. When a portoenterostomy or liver transplant occurs, sections of the liver, biliary remnant and bile specimens, if removed in the course of surgery and in excess of that needed for diagnostic use, will be sent for the repository. These specimens will be used in investigations into the mechanisms and causes of the liver damage that occur in the subject's condition. As part of the standard of care, the study will follow-up and record progress of the liver problem by routine clinical examinations and laboratory tests for up to 15 years. All data from this study will be kept in a secure research database at the data coordinating center.

This multi-center network of investigators will address issues of etiology, pathogenesis, natural history, diagnosis, and novel treatments for one of the most devastating pediatric illnesses that occur in the first few months of life, biliary atresia, and related disorders such as idiopathic neonatal hepatitis. Although these disorders are not common, the effects on children, siblings, and their families and the frequent need for liver transplantation, mandate a greater degree of attention by the scientific community than in the past. Moreover, knowledge gained from these investigations has a high likelihood of affecting diagnosis and treatment of adults with cholestatic liver disease and improving our understanding of fundamental processes regulating bile flow, cytoprotection, and liver and biliary development. The development of a serum and tissue bank of specimens from children with various neonatal cholestatic disorders will be an invaluable tool for current and future investigations into the etiology and pathogenesis of hepatobiliary injury in the infant.

4.2 Enrollment of Subjects

The study population to be enrolled will consist of male and female infants less than or equal to 180 days old. All racial and ethnic groups will be included.

4.2.1 Inclusion Criteria

- Infant's age less than or equal to 180 days at initial presentation at the ChiLDREN clinical site.
- Diagnosis of cholestasis defined by serum direct or conjugated bilirubin greater than 20% of total and greater than or equal to 2 mg/dl.
- The subject's parent(s)/guardian(s) willing to provide informed written consent.

4.2.2 Exclusion Criteria

- Acute liver failure.
- Previous hepatobiliary surgery with dissection or excision of biliary tissue.
- Diagnoses of bacterial or fungal sepsis (except where associated with metabolic liver disease)
- Diagnoses of hypoxia, shock or ischemic hepatopathy within the past two weeks (If the cholestasis persists beyond two weeks of the initiating event, the infant can be enrolled).
- Diagnosis of any malignancy.
- Presence of any primary hemolytic disease (except when diagnosed with biliary atresia or another cholestatic disease being studied by ChiLDREN).
- Diagnosis of any drug or TPN-associated cholestasis (except when diagnosed with biliary atresia or another cholestatic disease being studied by ChiLDREN).
- Diagnosis with ECMO-associated cholestasis.
- Birth weight less than 1500g (except when diagnosed with biliary atresia).

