4. To identify risk factors (such as, environmental, infectious and genetic risk factors) related to onset, to outcome and to the success of treatment(s) for the different cholestatic diseases, with special emphasis on biliary atresia.

3. Background

Clinical Significance of Biliary Atresia and Idiopathic Neonatal Hepatitis

Neonatal cholestatic disorders are a group of hepatobiliary diseases occurring within the first three months of life in which bile flow is impaired and characterized by conjugated hyperbilirubinemia, acholic stools, and hepatomegaly. Overall, 1 in 2500 live births is affected with a neonatal cholestatic disorder. The two most common causes of neonatal cholestasis are biliary atresia and idiopathic neonatal hepatitis. Other causes include a variety of metabolic and genetic diseases, known infections, progressive familial intrahepatic cholestatic disorders, paucity of interlobular bile ducts, and many others. Biliary atresia is the most common of these disorders, occurring in approximately 1 in 8000 to 1 in 15,000 live births, and characterized by complete fibrotic obliteration of the lumen of the extrahepatic biliary tree within three months of life¹. A recent study suggested that the prevalence of biliary atresia may be higher in African-American children than in Caucasian children². Fibrous obliteration may involve the entire extrahepatic biliary system or any part of the system, with injury and fibrosis of intrahepatic bile ducts as well (hence the term "extrahepatic" has been dropped in

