Although biliary atresia and idiopathic neonatal hepatitis are the main focus of this project, there are many other causes of neonatal cholestasis that may be investigated by the Childhood Liver Disease and Research Network potentially leading to new knowledge and understanding of hepatocyte and biliary physiology and pathophysiology¹⁰. Recent identification of the genetic and molecular causes of several forms of progressive familial intrahepatic cholestasis (PFIC) (e.g., mutations in genes coding for BSEP, FIC1, and MDR3)¹¹ has not only provided explanation for etiology of these rare but devastating disorders, but moreover, has led to the discovery of new bile acid and phospholipid membrane transporters. This new knowledge has revolutionized our understanding of mechanisms of bile flow, predisposition to gallstone disease, and role of heterozygote states in these and other genes modifying or causing other hepatobiliary diseases^{12,13}. Alagille syndrome, alpha-1 antitrypsin deficiency, cystic fibrosis liver disease, TPN-related cholestasis, choledochal cyst and PFIC are other disorders worthy of investigation by this Network. Because infants and young children with other causes of neonatal cholestasis will be required as “disease controls” in the proposed database, a cohort of children with other relevant neonatal liver diseases will be tracked during this study and will be available for additional investigation.

Diagnosis, Treatment And Outcome – Current Limitations

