4.2.3 Exceptions to the Inclusion/Exclusion Criteria

Infants with biliary atresia with a birth weight of less than 1500 g may be included in the database. The investigator should request permission for a protocol exemption when biliary atresia is suspected. If the diagnosis is subsequently not confirmed, the infant will become ineligible.

Similarly, infants with a hemolytic disorder, or a diagnosis of any drug or TPN-associated cholestasis, who have biliary atresia or another cholestatic disease being studied by ChiLDREN may be included in the database. The investigator should request permission for a protocol exemption for these cases. If the diagnosis is subsequently not confirmed, the infant will become ineligible.

When an eligible diagnosis, such as metabolic liver disease, is suspected but is not yet ascertained at the time of initial evaluation, the infant should be recruited into the database; the infant will become ineligible if the diagnosis subsequently does not confirm cholestatic disease.

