It is anticipated that the 15 ChiLDREN clinical sites combined will accrue approximately 40 cases of biliary atresia annually and an equal number of cases of patients with cholestasis with a different etiology. If 75% of the eligible subjects are recruited into the observational database, there will be 30 cases per year of biliary atresia and a similar number with other diseases. The intention of the observational database is to continue to accrue subjects as long as possible—therefore, the sample size is a function of the available subjects and length of accrual. Using data from these subjects, ChiLDREN desires to estimate the incidence of the failure of treatment, factors associated with success/failure, etc.

In the table below we indicate the relationship between sample size and effect size at a fixed power. We assume that we will be comparing infants with biliary atresia to control infants when computing effect size and difference in proportions and that we are trying to identify association of covariates with outcomes for infants with biliary atresia (one sample only) in the last column. All estimates are for 80% power using a two-tailed tests at a 5% level of significance. The effect size is the expected difference between two groups divided by the standard deviation. The difference of proportions is computed for the case where one group has a proportion of 50%; the difference will be smaller when the groups have proportions nearer to zero or one.

For example, it is possible that patients with biliary atresia have a 40% rate of reovirus compared to 20% in the controls. With 85 subjects per group, or after approximately 3 years of patient accrual, there will be 80% power to observe this difference. (This differs from the table below, because we used a worst case scenario, differences from 50%, to compute the entries in the table.) Factors that are hypothesized to affect success of the portoenterostomy are age (in weeks) at the time of the portoenterostomy and the number of episodes of cholangitis after the portoenterostomy; if the association between these factors and length of time to transplant or death is 0.3 or greater, we will be able to identify this correlation with 80% power when 90 subjects with biliary atresia have been studied.

The sample size needed to test the specified effect size or difference in proportions when comparing two groups or to identify the specified correlation in a single group.

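### Infants under 1500 g can enter the biliary atresia group but never the control group, so comparisons of birth weight and its close correlates are biased unless restricted to 1500 g or more

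*Supplement*

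**What the plan says.** - **Eligibility.** The birth-weight exclusion in Section 4.2.2 reads "Birth weight less than 1500g (except when diagnosed with biliary atresia". Section 4.2.3 gives the route in: "The investigator should request permission for a protocol exemption when biliary atresia is suspected". It also gives the route out: "If the diagnosis is subsequently not confirmed, the infant will become ineligible".
- **A contrast in the same list.** The drug/TPN exclusion has a wider exception: "Diagnosis of any drug or TPN-associated cholestasis (except when diagnosed with biliary atresia or another cholestatic disease being studied by ChiLDREN". The hemolytic-disease exception is equally wide. Of these three, only the birth-weight exception is reserved for biliary atresia.
- **Who the controls are.** Section 3 says that infants with other causes of neonatal cholestasis are needed as disease controls, and that "a cohort of children with other relevant neonatal liver diseases will be tracked during this study". They enrol under this protocol and its criteria.
- **Purpose.** Aim 4 in Section 2 is "To identify risk factors (such as, environmental, infectious and genetic risk factors) related to onset, to outcome and to the success of treatment(s", with special emphasis on biliary atresia.
- **Planned comparison.** Section 6, Sample Size and Accrual: "We assume that we will be comparing infants with biliary atresia to control infants".
- **Data.** Section 4.4 records birth weight, prenatal history, labor and delivery, and complications of the newborn.
- **Analysis rules.** Section 6 does not restrict, match or stratify on birth weight. Its nearest rule, under Baseline comparisons, adds as covariates the baseline measures on which groups differ. That rule is worded for treatment groups and treatment efficacy.

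**The concern.** Eligibility depends jointly on diagnosis and on a perinatal variable. In an onset comparison, diagnosis defines cases and controls, and perinatal variables are among the candidate exposures. The control share below 1500 g is therefore zero by rule, whatever it is among infants with other cholestatic diseases. Any exposure more common below 1500 g will look more frequent in biliary atresia even if, at a given birth weight, cases and controls do not differ.

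The direction could mislead. Section 3 describes infants with idiopathic neonatal hepatitis as frequently small for gestational age and those with biliary atresia as appropriately grown. If other-cholestasis infants are in truth the more likely to weigh under 1500 g, the eligibility rule can reverse the sign of the birth-weight difference.

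**Working it through.** **1. The plan's own figure.** Inputs from Section 6: 85 per group, 40% versus 20%, two-sided 5%, stated power 80%.

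Power = Φ[(d − 1.96·SE0)/SE1], with d = 0.20, SE0 = √(2·0.3·0.7/85) = 0.0703 and SE1 = √((0.4·0.6 + 0.2·0.8)/85) = 0.0686. This gives Φ(0.907) = 81.8%, which agrees with the stated 80%.

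**2. Who can be in each group.** Reading 4.2.2 with 4.2.3:

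| | Birth weight ≥1500 g | Birth weight <1500 g |
|---|---|---|
| Biliary atresia | eligible | eligible by exemption |
| Other cholestasis | eligible | excluded, or removed once biliary atresia is not confirmed |

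**3. Size of the bias.** Let v be the share of enrolled biliary atresia infants under 1500 g, and e0 and e1 the exposure rates at ≥1500 g and <1500 g. Suppose cases and controls do not differ within either birth-weight stratum. Then

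- P(exposed | biliary atresia) = (1 − v)·e0 + v·e1
- P(exposed | control) = e0
- spurious difference = v·(e1 − e0)

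The documents give none of v, e0 or e1. All values below are assumptions, set out as ranges. Type I error is the chance of a two-sided 5% rejection with 85 per group.

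| Exposure (e0, e1) | v = 1% | v = 5% | v = 10% |
|---|---|---|---|
| Unrelated (20%, 20%) | OR 1.00; 5.0% | OR 1.00; 5.0% | OR 1.00; 5.0% |
| Moderately linked (20%, 40%) | OR 1.01; 5.0% | OR 1.06; 5.3% | OR 1.13; 6.2% |
| Strongly linked (20%, 80%) | OR 1.04; 5.1% | OR 1.20; 7.6% | OR 1.41; 15.3% |
| Near-marker (10%, 90%) | OR 1.09; 5.3% | OR 1.47; 12.6% | OR 1.98; 32.3% |

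One cell in full (strongly linked, v = 5%): 0.95·0.20 + 0.05·0.80 = 0.23 against 0.20, so OR = (0.23/0.77)/(0.20/0.80) = 1.195. At v = 3% the strongly linked type I error is 6.0%.

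A larger sample does not dilute the bias. At 150 per group, the year-5 row of the Section 6 table, the strongly linked figures are 9.7% (v = 5%) and 23.4% (v = 10%).

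**4. Birth weight under 1500 g as the factor itself.** The control count is forced to 0. Fisher's exact test at 90 per group gives p = 0.059 for 5 versus 0, 0.029 for 6 versus 0 and 0.003 for 9 versus 0. Five to nine infants are about 5% to 10% of 90. For the sign: with assumed true shares of 3% in biliary atresia and 10% in other cholestasis, the true difference is 3 − 10 = −7 points, and the observed one is 3 − 0 = +3 points.

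**5. Cost of restricting.** Removing infants under 1500 g leaves 85·(1 − v) in the biliary atresia group against 85 controls. Power for 40% versus 20%:

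| v | Biliary atresia n | Power |
|---|---|---|
| 1% | 84.2 | 81.6% |
| 3% | 82.5 | 81.2% |
| 5% | 80.8 | 80.8% |
| 10% | 76.5 | 79.8% |

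The loss from 81.8% is at most 2.0 points over this range.

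**The case against.** The strongest reply has four parts.

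**The effect may be negligible.** The share of biliary atresia infants under 1500 g is unknown, and Section 3 describes these infants as appropriately grown, which gives no support to a high share. Aim 4's examples are environmental, infectious and genetic factors, and the worked example is reovirus. This stands as a limit on size. Where exposure is unrelated to very low birth weight there is no bias, and a moderate link gives an odds ratio of at most 1.06 for shares up to 5%. A reader might infer that every comparison of perinatal factors is biased by the rule; the calculation does not support that.

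**The plan already adjusts for baseline differences.** Birth weight is a baseline variable, so the covariate rule might pick it up. This stands only in part. The rule is written for treatment efficacy, and with no controls below 1500 g a model can only extrapolate there.

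**This is a database protocol, and specific comparisons are left to ancillary studies.** No separate SAP is shown, and Section 4.5.2 says that no proposed ancillary study was yet approved. Because birth weight is recorded, any analyst could restrict later, so no lasting harm is done. That is fair as to reversibility. But Section 6 itself sets up the comparison with controls and lays down general rules for group comparisons. Followed as written, those rules leave the asymmetry in.

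**Two tempting extensions fail.** A reader might treat the hemolysis and drug/TPN exemptions as the same fault. They are not, because they also admit other cholestatic diseases under study. Nor do the documents show that controls concentrate below 1500 g: small for gestational age is a relative measure, and 1500 g is an absolute cut-off.

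**Conclusion.** The point holds for a limited set of comparisons. By rule, the control group contains no infant under 1500 g while the biliary atresia group may, and nothing in Section 6 deals with this. Onset comparisons of birth weight and of factors closely tied to it are biased by selection, and for birth weight itself the sign can reverse.

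The size rests on assumed shares and exposure rates. It is small at a share of 1% to 2%. At 5% to 10% the type I error for a strongly linked exposure is 7.6% to 15.3% at 85 per group, and it is higher for a near-marker of very low birth weight. Admitting biliary atresia infants under 1500 g is reasonable for describing natural history. The fault is the missing analysis rule. It should be corrected, because the correction is cheap and uses data already collected.

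**What to change.** Add to Section 6:

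- Onset and risk-factor comparisons of biliary atresia with other cholestasis use, as the primary analysis, infants with birth weight of at least 1500 g in both groups.
- The comparison of all enrolled infants is reported as a sensitivity analysis, with the number of biliary atresia infants under 1500 g stated.
- Biliary atresia infants under 1500 g stay in the natural-history and outcome analyses within biliary atresia.

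Infants admitted under the hemolysis or drug/TPN exemptions need not be removed. Eligibility and data collection do not change.

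The cost is a few biliary atresia infants in these comparisons: 0.3 to 3 of the 30 expected per year at shares of 1% to 10%, and at most about 2 points of power at the 10% share. The restricted result applies to infants of 1500 g or more. Whether very low birth weight is itself a risk factor cannot be answered from these two groups, and the plan should say so.
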